Version Date: 06/05/2017

Abbreviated Title: Adrenal Neoplasm

CC Protocol: 11-C-0149 D

Version Date: 06/05/2017

NCT Number: NCT01348698

Title: Evaluation of Diagnostic and Prognostic Molecular Markers in Adrenal Neoplasm

NCI Principal Investigator: [name] ^{A-F}
EOB/CCR/NCI
[name]
[name]
[name]
[contact]
[contact]

NCI Associate Investigators: [name], LP/CCR/NCI ^{E-F}
[name], EOB/CCR/NCI ^{A-F}
[name], OCD/CCR/NCI ^{A-C, E-F}
[name], OCD/CCR/NCI ^{E-F}
[name], EOB/CCR/NCI ^{A-F}
[name], MD, EOB/CCR/NCI ^{A-F}
[name], CRNP, EOB/CCR/NCI ^{A-C, E-F}
[name] [name], OCD/CCR/NCI ^{A-C, E-F}
[name], EOB/CCR/NCI ^{A-F}
[name], EOB/CCR/NCI ^{A-F}

Referral Contact/

Study Coordinator:

[name]
[name]
[name]
[contact]
Email: [contact]

Investigators Roles

- A. Obtain information by intervening or interacting with living individuals for research purposes
- B. Obtaining identifiable private information about living individuals
- C. Obtaining the voluntary informed consent of individuals to be subjects
- D. Makes decisions about subject eligibility
- E. Studying, interpreting, or analyzing identifiable private information or data/specimens for research purposes
- F. Studying, interpreting, or analyzing de-identified data or specimens for research purposes
- G. Some/all research activities performed outside NIH

PRÉCIS

Background:

- Adrenal neoplasms are common and are incidentally discovered in 4-10% of abdominal imaging studies.
- The majority of adrenal incidentalomas are cortical adenoma.
- Many patients with nonfunctioning adrenal incidentalomas undergo adrenalectomy to exclude a cancer diagnosis.
- There are no reliable clinical, radiographic or laboratory studies that accurately distinguish between localized benign and malignant adrenal neoplasm.
- This protocol is designed to determine the feasibility and accuracy of using novel molecular markers of malignant adrenal neoplasm in fine needle aspiration (FNA) biopsy and surgically resected samples.

Objectives:

- Primary Objectives:
 - To evaluate the feasibility of molecular testing in adrenal neoplasm FNA biopsy samples.
 - To determine the accuracy of novel diagnostic molecular markers in clinical adrenal FNA biopsy and surgically resected samples.
- Secondary Objectives
 - To analyze the gene expression level relative to disease-free survival and overall survival in patients with adrenocortical carcinoma

Eligibility:

- An individual with an adrenal neoplasm greater than 2 cm in size
- Age \geq 18 years
- Adults must be able to understand and sign the informed consent document

Design:

- Prospective observational study.
- Demographic, clinical, laboratory and pathologic data will be collected for each patient participant. Data will be securely stored in a computerized database.
- Patients will have biochemical testing to determine if their adrenal neoplasm is functioning or nonfunctioning.
- After their initial on-study evaluation, patients who are found to have a nonfunctioning adrenal tumor with a low risk of malignancy will be re-screened every year for 5 years with non-invasive imaging studies.

Abbreviated Title: Adrenal Neoplasm

Version Date: 06/05/2017

- Treatment of patients with an adrenal neoplasm will be performed based on standard clinical practice.
- Projected accrual will be 50 patients per year for a total of 10 years. Thus, we anticipate accruing 500 patients on this protocol.

TABLE OF CONTENTS

Précis.....	3
Table of Contents.....	5
1 Introduction	7
1.1 Study Objectives	7
1.2 Background and Rationale	7
2 Eligibility Assessment and Enrollment	8
2.1 Inclusion Criteria.....	8
2.2 Exclusion criteria.....	9
2.3 Registration procedures.....	9
3 Study Implementation.....	9
3.1 On Study Evaluation	10
3.2 CT guided fine needle aspiration biopsy of adrenal neoplasm	10
3.3 Surgical Intervention	10
3.4 Follow-up Examinations	11
3.5 Off Study Criteria.....	12
4 Concomitant medications/measures	12
5 BIOSPECIMEN COLLECTION	13
5.1 CORRELATIVE STUDIES FOR RESEARCH/PHARMACOKINETIC STUDIES	13
5.2 SAMPLE STORAGE, TRACKING AND DISPOSITION.....	14
6 Data Collection and Evaluation.....	14
6.1 Data Collection.....	14
6.2 Data Sharing Plans	15
6.3 Toxicity Criteria	15
7 SAFETY Reporting REQUIREMENTS/DATA AND SAFETY MONITORING PLAN	15
7.1 DEFINITIONS.....	15
7.2 NCI-IRB AND Clinical Director Reporting	17
7.3 Data and Safety Monitoring Plan	18
8 Statistical Considerations	18
9 Human Subjects Protections.....	19
9.1 Rationale for subject selection	19

9.2	Participation of Children	19
9.3	Participation of Subjects unable to give consent.....	19
9.4	Evaluation of Benefits and Risks/Discomforts	19
9.5	Consent Process and Documents.....	20
10	References.....	22
11	APPENDICES	25
11.1	Appendix A.....	25
11.2	Appendix B.....	28
11.3	Appendix C.....	29

1 INTRODUCTION

1.1 STUDY OBJECTIVES

1.1.1 Primary Objectives:

- To evaluate the feasibility of molecular testing in adrenal neoplasm FNA biopsy samples.
- To determine the accuracy of novel diagnostic molecular markers in clinical adrenal FNA biopsy and surgically resected samples.

1.1.2 Secondary Objectives

- To analyze the gene expression level relative to disease-free survival and overall survival in patients with adrenocortical carcinoma

1.2 BACKGROUND AND RATIONALE

Adrenal neoplasms are one of the most prevalent of all human tumors [1]. The prevalence of adrenal incidentaloma is approximately 5% on abdominal imaging, but the prevalence can be as high as 10% in the elderly. As the U.S. population ages, the management of adrenal incidentaloma will be an increasingly important issue in health care [1]. As outlined in a NIH State-of-the-Science statement on the “Management of the Clinically Inapparent Adrenal Mass (Incidentaloma)” there are significant limitations in diagnostic evaluation of these tumors because there are no reliable criteria for predicting the risk of malignancy, outside of obvious metastatic or locoregional disease [2]. This results in many patients having adrenalectomy to exclude a cancer diagnosis [3, 4]. For this reason, we will test the feasibility and determine the accuracy of novel diagnostic molecular markers in adrenal neoplasm FNA biopsy and in surgical resected samples.

There are no reliable preoperative clinical, imaging or biochemical tests available to distinguish between primary benign and malignant adrenocortical neoplasms in the absence of obvious metastatic disease or locoregional invasion [5]. Imaging features such as tumor heterogeneity, irregular tumor border, hemorrhage, necrosis, rapid tumor growth rate, tumor Hounsfield unit $>10-20$ on non-contrast CT scan, and intravenous contrast washout of 40% or less after 15 minutes are more common in malignant tumors but are not reliable enough to avoid the need for adrenalectomy to exclude a cancer diagnosis nor to forgo continued follow up [5-10]. In patients with a history of an extra-adrenal malignancy, an adrenal incidentaloma may indicate metastatic disease in 32% to 73% of cases depending on the primary tumor site and patient age [1, 11]. The tumor size of adrenal neoplasm measured by imaging studies has been used as a preoperative surrogate marker for a malignant tumor and for recommending resection, but this criterion is not precise for tumors that measure > 2 cm but < 6 cm [2, 12]. Even when the tumor is 6 cm or larger, the reported risk of malignancy ranges from 5% to 98%, depending on the study cohort [5, 13, 14]. In many centers, a size threshold of > 6 cm has been used as an absolute indication for adrenalectomy. However, it is unclear whether adrenal tumors between 2 cm and 6 cm should be removed or monitored, whereas most experts recommend monitoring tumors < 4 cm in size depending on the patient’s age.

Fine needle aspiration biopsy and cytologic examination has not been routinely used to evaluate adrenal neoplasm at most centers because it is not accurate enough for

distinguishing between primary benign and malignant adrenocortical tumors [15-19]. However, in patients with a concurrent malignancy or history of extra-adrenal malignancy, fine needle aspiration biopsy may be useful for detecting metastatic disease to the adrenal gland after biochemical exclusion of a hyperfunctioning tumor, especially a pheochromocytoma [15-19]. Fine needle aspiration of the adrenal gland is associated with a low risk (<1%) of complications such as bleeding, pneumothorax, pain, and rarely tumor seeding along the needle track [1, 20].

Postoperative histopathologic examination to distinguish between malignant and benign primary adrenal tumors is also difficult and problematic. For adrenocortical neoplasms, the Weiss histologic criterion is most commonly used, but is imprecise [21-23]. This means even patients with histologically diagnosed adrenocortical adenoma require continued follow-up because some will develop metastatic disease [11].

In summary, although adrenocortical carcinomas tend to be larger than benign tumors, tumor size, even when combined with imaging features, is not accurate enough to use for making management decisions for most tumors that are less than 6 cm. Furthermore, imaging studies such as MRI and CT scans underestimate adrenal tumor size by 16% to 47%, and are less accurate in smaller tumors [24-26]. Therefore, there is a significant need for biomarkers that can distinguish benign from malignant adrenal tumors for determining the need for adrenalectomy, for selecting the appropriate surgical approach, and for determining the appropriate follow up.

We and others have used genome profiling approaches (mRNA, microRNA) to identify diagnostic and prognostic markers of malignant adrenocortical tumors [27-31]. In our studies, we have identified several novel diagnostic markers with excellent accuracy for distinguishing between benign and primary malignant adrenocortical tumors ([Appendix A](#)). While these markers could be used in post-surgical resection samples in equivocal cases, the most helpful clinical application of these markers would be preoperatively in clinical fine needle aspiration biopsy samples. Therefore, we propose to test the feasibility and accuracy of using this panel of markers in fine needle aspiration samples of patients with adrenal neoplasm with the exception of pheochromocytoma that are greater than 2 cm. For cytologic examination, fine needle aspiration biopsy has a 67%-100% adequacy rate [32, 33]. Our previous studies in thyroid fine needle aspiration biopsy samples indicate an adequate yield of nucleic acid for multigene expression analysis [34]. Moreover, we are able to determine gene expression levels in as little as 10 adrenocortical carcinoma cells by quantitative RT PCR ([Appendix B](#)).

2 ELIGIBILITY ASSESSMENT AND ENROLLMENT

2.1 INCLUSION CRITERIA

- a. An individual with a primary localized adrenal neoplasm greater than 2 cm in size
- b. Age \geq 18 years
- c. Adults must be able to understand and sign the informed consent document
- d. Patients must have an ECOG performance score of 0-2.

e. Patients must have laboratory and physical examination parameters within acceptable limits by standard of practice guidelines prior to biopsy or surgery

Note: patients with suspected but unconfirmed adrenal neoplasm may be enrolled.

2.2 EXCLUSION CRITERIA

[figure not shown]
- a. Biochemically proven Pheochromocytoma
- b. Women who are pregnant because of the possible side effects of radiation from CT-guided biopsies to the unborn child.

2.3 REGISTRATION PROCEDURES

Authorized staff must register an eligible candidate with NCI Central Registration Office (CRO) within 24 hours of signing consent. A registration Eligibility Checklist from the web site (<http://home.ccr.cancer.gov/intra/eligibility/welcome.htm>) must be completed and sent via encrypted email to: NCI Central Registration Office (HOIS) [contact]. After confirmation of eligibility at Central Registration Office, CRO staff will call pharmacy to advise them of the acceptance of the patient on the protocol prior to the release of any investigational agents. Verification of Registration will be forwarded electronically via e-mail to the research team. A recorder is available during non-working hours.

3 STUDY IMPLEMENTATION

This is a prospective study of individuals with an adrenal mass. Individuals will have routine clinical work up for an adrenal mass (see section 3.1); those with nonfunctioning tumors larger than 2 cm will undergo CT guided fine-needle aspiration biopsy. For patients who require adrenalectomy for a functioning tumor, the surgically resected tissue sample will be used for the molecular analysis.

3.1 ON STUDY EVALUATION

Patients will undergo the following evaluations which may be performed within 4 weeks of enrollment:

[figure not shown]
- Detailed History and Physical Examination including, vital signs, ECOG status, demographic information and family history.
- Imaging studies
 - Adrenal protocol CT scan with and without intravenous contrast.
 - FDG PET/CT scan
- Laboratory evaluations
 - CBC with differential
 - Sodium (Na), Potassium (K), Chloride (Cl), Total CO₂ (bicarbonate), Creatinine, Glucose, Urea nitrogen (BUN), Albumin, Calcium total, Magnesium total (Mg), Inorganic Phosphorus, Alkaline Phosphatase, ALT/GPT, AST/GOT, Total Bilirubin, Direct Bilirubin, LD, Total Protein, Total CK, Uric Acid
 - PT/PTT
- Biochemical testing
 - Serum renin and plasma aldosterone levels
 - 24-hour urinary cortisol level
 - Low dose (1-2mg) dexamethasone suppression test
 - Serum fractionated plasma normetanephrine and metanephrine

3.2 CT GUIDED FINE NEEDLE ASPIRATION BIOPSY OF ADRENAL NEOPLASM

- Patients with confirmed non-functional tumors greater than 2 cm in greatest dimension will undergo CT guided fine needle aspiration in the Interventional Radiology Department as per standard of care if they do not require an adrenalectomy.
- Tissue will be handled as described in Section [5.1.1](#)

3.3 SURGICAL INTERVENTION

Patients with an adrenal neoplasm will have an adrenalectomy based on our standard clinical practice ([Appendix C*](#)).

*Patients with an adrenal mass measuring 2 – 4cm and suspicious imaging features for malignancy will be given the option of adrenalectomy.

3.4 FOLLOW-UP EXAMINATIONS

3.4.1 Patients who are found to have an adrenal neoplasm which does not require resection will undergo the following evaluations every year for 5 years:

- Physical exam to include vital signs and ECOG status
- Laboratory evaluations - all tumors
 - 24-hour urinary cortisol level
 - Low dose (1-2mg) dexamethasone suppression test
 - Serum fractionated plasma normetanephrine and metanephrine
 - Serum renin and plasma aldosterone levels
- Adrenal protocol CT scan with and without intravenous contrast.

3.4.2 Patients who undergo an adrenalectomy will undergo the following evaluations every year for 5 years (only if found to be malignant on histopathology):

- Physical exam to include vital signs and ECOG status
- Laboratory Evaluations
 - 24-hour urinary cortisol level
 - Low dose (1mg) dexamethasone suppression test (only for those patients with non-functioning tumors)
- CT scan of the chest, abdomen and pelvis to exclude disease recurrence

Note: Patients who are unwilling or unable to travel to the NIH Clinical Center for follow up may have the examinations performed at home with the results sent to the research team.

Note: Patients may be evaluated on a more frequent basis if they develop symptoms possibly associated with their adrenal neoplasm. Patients who meet the criteria for adrenalectomy at any time during the follow up period will be offered surgical intervention at the NIH Clinical Center. Patients who require chemotherapy will be offered a clinical trial at the NIH Clinical Center if they are eligible, or will be referred to their home oncologist for care.

3.5 OFF STUDY CRITERIA

Patients will be removed from the study if any of the following criteria are met:

- the patient requests withdrawal from the study
- the patient is consistently non-compliant with follow-up appointments
- the patient is consistently non-compliant with imaging studies.
- Completion of the protocol specified follow up period
- Loss of capacity to provide informed consent
- PI decision to close the study

3.5.1 Off Study Procedure

Authorized staff must notify Central Registration Office (CRO) when a subject is taken off protocol therapy and off-study. A Participant Status Updates Form from the web site (<http://home.ccr.cancer.gov/intra/eligibility/welcome.htm>) main page must be completed and sent via encrypted email to: NCI Central Registration Office (HOIS) [contact].

4 CONCOMITANT MEDICATIONS/MEASURES

Supportive care will be provided to the patients as is indicated by their endocrine neoplasm and procedures performed. The clinical evaluations done as part of this protocol may detect an unsuspected malignancy or other serious medical conditions. When this occurs, referral for treatment is expedited. If a participant requires cancer treatment and meets the eligibility criteria for an active CCR protocol, we will try to facilitate the referral process, but we cannot promise study participants treatment as part of the protocol. Otherwise, referral is made to qualified therapists at regional cancer centers or in the patient's home community.

5 BIOSPECIMEN COLLECTION

5.1 CORRELATIVE STUDIES FOR RESEARCH

5.1.1 Adrenal biopsy and surgical specimens

The adrenal fine needle aspiration will be performed at the NIH Clinical Center. Patients will undergo one biopsy. A portion of the FNA sample will be sent to the department of pathology, and the remainder to the Endocrine Oncology laboratory. The biopsy sample will be immediately placed in RNAlater®, transported on ice, and stored in -80°C until used for molecular analysis. For the surgical resection specimen, the samples will be immediately snap frozen in liquid nitrogen and stored in -80°C until molecular analysis.

Samples will be immediately transported to:

NCI Endocrine Oncology Laboratory
[name]
[name]
[name]
[contact]

[figure not shown]

Figure 1. Flow diagram of specimen collection and analysis.

The diagnostic accuracy of the candidate gene expression levels will be determined based on the histologic diagnosis and follow up time of over 5 years. We will also analyze the gene expression level relative to disease-free survival and overall survival in patients with adrenocortical carcinoma. All the candidate gene expression level thresholds/cutoffs will be normalized to an adrenocortical carcinoma cell line and universal RNA to account for interassay variability.

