9 HUMAN SUBJECTS PROTECTIONS

9.1 RATIONALE FOR SUBJECT SELECTION

Subjects will be selected for this protocol based on a clinical diagnosis of an adrenal neoplasm. Only patients at low risk for a malignant tumor will undergo fine needle aspiration biopsy and those requiring an adrenalectomy will have surgical resected tissue to test the markers. Such a selection criteria for performing the fine needle aspiration biopsy would allow us to select those patients most likely to represent a diagnostic dilemma and to benefit from such an analysis.

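### Resected tumours read as benign have no protocol-scheduled follow-up, although Section 5.1.1 rests diagnostic accuracy on histology and follow-up and Section 1.2 calls the histologic criterion imprecise

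*Combined protocol and SAP*

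**What the plan says.** **Reference standard.** Section 5.1.1 states that the accuracy of the candidate markers "will be determined based on the histologic diagnosis and follow up time of over 5 years". Section 8 plans precision for 35 malignant and 200 benign masses by their eventual status. It does not say what evidence settles that status.

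**Follow-up.** Section 3.4.1 provides that patients with "an adrenal neoplasm which does not require resection will undergo the following evaluations every year for 5 years". Section 3.4.2 gives adrenalectomy patients evaluations "every year for 5 years (only if found to be malignant on histopathology". The Précis mentions re-screening only for nonfunctioning tumours at low risk of malignancy.

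**Who is in the marker analysis.** Section 3: "For patients who require adrenalectomy for a functioning tumor, the surgically resected tissue sample will be used for the molecular analysis". Section 9.1 adds that "those requiring an adrenalectomy will have surgical resected tissue to test the markers".

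**Histology.** Section 1.2 says that "the Weiss histologic criterion is most commonly used, but is imprecise", and that "even patients with histologically diagnosed adrenocortical adenoma require continued follow-up because some will develop metastatic disease".

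**Other relevant text.** Section 7 promises standard-of-care follow-up for all patients, without a schedule, a duration or a link to the accuracy analysis. Section 3.5 takes patients off study when their specified follow-up period ends, but names no period for a benign resection.

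**The concern.** A resected tumour read as benign falls outside both arms of Section 3.4, yet its tissue is used to test the markers. Section 3.4.2 therefore withholds, for this one group, the follow-up that Section 5.1.1 names and that Section 1.2 says histologic adenomas need.

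Accuracy is a primary objective. If a cancer is misread as adenoma, no planned data would correct the label. It would count as a true negative if the marker missed it, and as a false positive if the marker detected it. In both cases it would also be absent from the sensitivity denominator.

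Benign labels backed by 5 years of scheduled imaging would be pooled with benign labels that may rest on one histologic reading, in a single specificity and a single AUC. For a fixed misread rate, a larger sample does not reduce this error.

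**Working it through.** **1. The texts by patient group**

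| Group | Tissue in marker analysis | Scheduled follow-up |
|---|---|---|
| Unresected | FNA (3, 3.2) | Yearly, 5 years (3.4.1) |
| Resected, read as malignant | Resected tissue (3, 9.1) | Yearly, 5 years (3.4.2) |
| Resected, read as benign | Resected tissue (3, 9.1) | None stated |

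Section 5.1.1 can be read by route: histology if resected, follow-up if not. On that reading 5.1.1 and 3.4.2 agree. The conflict between 1.2 and 3.4.2 remains, and so does the undefined standard in Section 8. Separately, 5.1.1 asks for more than 5 years, while 3.4 schedules 5.

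**2. The plan's own precision (Section 8)**

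Half-width = 1.96 × √(0.9 × 0.1 / n).
- n = 35: 9.9 points.
- n = 200: 4.2 points.

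Both stated figures reproduce. They treat true status as known without error.

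**3. Illustration of label error**

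From Section 8: 35 recognised cancers, 200 read-benign cases, and 90% for both sensitivity and specificity. Here the 90% is taken as the sensitivity seen in the 35 recognised cancers and as the specificity in truly benign cases.

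Assumed, because the documents give no values:
- m = number of misread cancers among the 200, from 1 to 6. This corresponds to 2% to 4% of 50, 100 or 150 resected-benign cases.
- d = share of the misread cancers that the marker detects, from 0 to 1.

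True sensitivity = (31.5 + d·m)/(35 + m), so the overstatement is m(0.9 − d)/(35 + m).

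Labelled specificity = [0.9(200 − m) + (1 − d)m]/200, so the understatement is m(d − 0.1)/200.

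| m | Sensitivity overstated, d = 0 | Sensitivity understated, d = 1 | Specificity overstated, d = 0 | Specificity understated, d = 1 |
|---|---|---|---|---|
| 1 | 0.9/36 = 2.5 | 0.1/36 = 0.3 | 0.1/200 = 0.05 | 0.9/200 = 0.45 |
| 2 | 1.8/37 = 4.9 | 0.2/37 = 0.5 | 0.2/200 = 0.1 | 1.8/200 = 0.9 |
| 4 | 3.6/39 = 9.2 | 0.4/39 = 1.0 | 0.4/200 = 0.2 | 3.6/200 = 1.8 |
| 6 | 5.4/41 = 13.2 | 0.6/41 = 1.5 | 0.6/200 = 0.3 | 5.4/200 = 2.7 |

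Results are in percentage points. The sensitivity shift changes sign at d = 0.9 and the specificity shift at d = 0.1, so the direction depends on a detection rate that nobody has stated. At m = 6 and d = 0 the sensitivity shift (13.2) exceeds the planned half-width (9.9). The specificity shift stays below 4.2 throughout this assumed range.

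**The case against.** The strongest reply is that 5.1.1 is meant by route, so histology is the intended standard for resected tumours and nothing is contradicted. Figure 1, the specimen flow diagram in 5.1.1, is not visible and might say so. This removes the clash between 5.1.1 and 3.4.2. It does not answer Section 1.2, and it leaves unequal labels pooled under an undefined standard in Section 8.

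Four stronger readings are tempting, and the documents do not support them:

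- **That these cases are analysed on histology alone.** No text says so. Section 7 promises standard-of-care follow-up, 6.1 includes review of records, and the notes to 3.4 allow extra evaluation for symptoms. What stands is that none of this is scheduled for the purpose or tied to the label.
- **That the case report form list in 6.1 shows recurrence goes uncaptured in this group.** That list omits histology and survival for every patient, although the Précis promises pathologic data and 5.1.1 plans survival analyses. It is a general point to clarify, not evidence about one group.
- **That the bias has a known direction or stays inside the planned intervals.** Both hold only if the detection rate is restricted, for example to 50% to 90%. Over the full range neither holds.
- **That the group is known to be large here.** Section 1.2 says "This results in many patients having adrenalectomy to exclude a cancer diagnosis", but that describes general practice. The resection algorithm in Appendix C is not visible.

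It is also fair to say that specificity by route cannot isolate the reference-standard error, because route is confounded with specimen type (FNA or resected tissue).

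**Conclusion.** The point holds and should be fixed, with moderate confidence. Following Section 3.4.2 as written leaves the benign labels of resected tumours in a primary accuracy analysis without scheduled verification, and Section 1.2 says that verification is needed. The finding rests on the wording of 1.2, 3.4, 5.1.1 and 8, not on the arithmetic.

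Neither size nor direction of bias is established, because the documents give no misread rate, no number of resected-benign cases and no marker detection rate for misread cancers. Under the assumed 1 to 6 misread cancers, the error in sensitivity runs from 13.2 points too high to 1.5 too low, and in specificity from 2.7 points too low to 0.3 too high. These figures show only that a handful of mislabelled cases can matter when about 35 cancers carry the sensitivity estimate.

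**What to change.** (a) In 5.1.1 and Section 8, define final status by route. For resected tumours, use histology updated by any recorded recurrence or metastasis. For unresected tumours, use the scheduled 5-year follow-up. Align the more-than-5-years wording in 5.1.1 with the 5-year schedule, and reconcile both with 1.2 and 3.4.2.

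(b) In 3.4.2 and 3.5, state the follow-up period for histologically benign resections. Capture recurrence and vital status passively from records over the same 5-year window, with no added examinations. In 6.1, make clear for all patients that histologic diagnosis, recurrence and vital status are in the analysis dataset.

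(c) In Section 8, keep the pooled specificity and add, descriptively, specificity for benign cases confirmed by scheduled follow-up and for those classified by histology with passive follow-up. State the confounding with specimen type. The split displays the difference in label quality but does not separate marker error from reference-standard error.

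**Cost.** A minor amendment, a small data-collection burden, and possible re-contact or consent for patients already off study. Passive capture is weaker than yearly scheduled CT, so verification stays unequal. Stratum intervals are wider: by 1.96 × √(0.09/n), the half-width at 90% is 8.3, 5.9 or 4.8 points for 50, 100 or 150 cases, against 4.2 for 200.
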